**ABBREVIATIONS**

Abbreviation	Term
AE	Adverse event
ALT	Alanine transaminase (also referred to as SGPT)
ANC	Absolute neutrophil count
APC	Antigen Presenting Cells
AST	Aspartate transaminase (also referred to as SGOT)
BUN	Blood urea nitrogen
CBC	Complete blood count
CD	Cluster of differentiation
CMV	Cytomegalovirus
CO 2	Total carbon dioxide
CR	Complete response
CRF	Case report form
CTCAE	Common Toxicity Criteria for Adverse Events
CTL	Cytotoxic T lymphocyte
DC	Dendritic cell(s)
DTH	Delayed-type hypersensitivity
ECOG PS	Eastern Cooperative Oncology Group Performance Score
ELISA	Enzyme-Linked ImmunoSorbent Assay
ELISPOT	Enzyme-Linked ImmunoSorbent Spot
ER	Endoplasmic reticulum
FANG™	bi-shRNA furin and GMCSF Augmented Autologous Tumor Cell Vaccine
FL	Flt-3-Ligand
GMCSF	Granulocyte Macrophage-Colony Stimulating Factor
GMP	Good Manufacturing Practice
GVAX	GMCSF Secreting autologous or allogenic tumor vaccine
HLA	Human Leukocyte Antigen
IBC	Institutional Biosafety Committee
IEC	Independent Ethics Committee
IL	Infiltrating lymphocytes
IRB	Institutional Review Board
LAK	Lymphokine-activated killer

Abbreviation	Term
LD	Longest diameter
LLC	Large latent complex
LPI	Lead Principal Investigator
MARY CROWLEY	Mary Crowley Cancer Research Centers
MHC	Major histocompatibility complex
MLR	Mixed lymphocyte reaction
MR	Mannose receptor
NCI	National Cancer Institute
NED	No evidence of disease
NK	Natural Killer
NKT	Natural Killer T cell(s)
NSCLC	Non small cell lung cancer
PCR	Polymerase chain reaction
PD	Progressive disease
PI	Principal Investigator
PR	Partial response
PS	Performance Status
RECIST	Response Evaluation Criteria in Solid Tumors
SCLC	Small cell lung cancer
SD	Stable disease
SLC	Small latent complex
STMN1	Stathmin 1
TAA	Tumor Associated Antigens
TAP	transporter associated with Ag processing
TGF $\beta$	Transforming growth factor- $\beta$
TIL	Tumor infiltrating lymphocytes
TNF	Tumor necrosis factor
Treg	Regulatory T cell
TTR	Time to recurrence
ULN	Upper limits of normal
WNL	Within normal limits

## SYNOPSIS

**Summary:** Despite a gradual improvement in their overall survival over the past decade, approximately 75% of women with Stage IIIC ovarian cancer who achieve a complete clinical response will relapse as will 50% of those achieving pathologic complete response at a median time of 18-24 months. Phase III studies of both maintenance and consolidation therapeutic interventions have not translated into an overall survival advantage. Preliminary studies of immunotherapy in patients with ovarian cancer suggest target accessibility (potential immunogenicity) to immune mediated approaches. In an effort to overcome limitations of immunostimulatory cancer vaccines, we designed a novel autologous whole cell vaccine, Vigil™ formerly known as FANG™, incorporating the rhGMCSF transgene and the bifunctional shRNAfurin (to block proprotein conversion to active TGFβ1 and β2) to 1) address the inability to fully identify cancer associated antigens, 2) effect antigen recognition by the immune system (i.e. antigen→immunogen), 3) enhance effector potency, and 4) subvert endogenous cancer-induced immune resistance.

A Phase I assessment of Vigil™ vaccine in 33 advanced solid tumor patients (1 of them being a pediatric patient 15 years of age) receiving ≥1 vaccination (at a dose of  $1.0 \times 10^7$  or  $2.5 \times 10^7$  cells/injection/month for a maximum of 12 vaccinations) demonstrated safety of the Vigil™ vaccine. Furthermore, proof of principle was established in the manufactured vaccines with increased mean GMCSF expression post-transfection to  $1135 \text{ pg}/10^6 \text{ cells/ml}$  and knockdown of furin, TGFβ1 and TGFβ2 at 78%, 93%, and 95%, respectively). In addition, although a Phase I study, the data suggested an overall survival benefit.

Given the preliminary Phase II evidence of prolongation of time to relapse in randomized Vigil™ vs. No Vigil™ treated patients ( $p=0.005$ ), as of this amendment all patients screening for enrollment into the main portion of the trial (including those who previously had tumor tissue harvested), will receive Vigil™ vaccine and will no longer be randomized. An extensive Phase II/III protocol is designed to more definitively assess benefit. Additional safety data in ovarian cancer patients receiving  $1 \times 10^7$  cells/ID injection on a monthly basis (maximum 12) is required.

This is a Phase II open-label study of maintenance intradermal autologous Vigil™ cancer vaccine administered to women with Stage III/IV epithelial ovarian cancer who attain a clinical complete response (including a post-treatment, prevaccination baseline serum CA-125 level of  $\leq 20 \text{ units/ml}$ ) after surgical cytoreduction and a total of six courses of front-line (pre- and post- or post-surgical) doublet chemotherapy. Patients meeting eligibility criteria will receive at least 5 but no more than 6 cycles of NCCN Category 1 chemotherapy. Thereafter, patients will receive Vigil™ vaccine at a dose of  $1.0 \times 10^7$  cells/injection for minimum of 4 to a maximum of 12 vaccinations (based on number of vaccine doses manufactured and patient eligibility). Trial endpoints

include time to recurrence (TTR), documentation of immune responses, and correlation of immune response and clinical effect.

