## 13.0 DATA EVALUATION

### 13.1 Statistics and Estimated Sample Size

The primary objective of this study is to investigate whether maintenance Vigil™ vaccine after a clinically defined complete response to induction platinum/paclitaxel chemotherapy results in prolonged time to recurrence (TTR) compared with standard of care observation. TTR was used for the purpose of sample-size estimation. Based on prior published experience (Markman, Liu et al. 2003), the median RFS after a clinical complete response to induction therapy for the control arm was estimated to be approximately 16 months for those with stage IV or suboptimal (> 1 cm residual) stage III disease and 24 months for stage III patients with optimal (< 1 cm residual) disease. Given an average RFS of 24 and 16 months, respectively, a 10% increase in RFS (i.e. TTR) would provide adequate statistical power to support expanding the study (Table 6). This analysis was performed using a statistical power calculator (<http://www.dssresearch.com/KnowledgeCenter/toolkitcalculators/statisticalpowercalculators.aspx>) to conduct a 1-tail test of a sample average in comparison to the historical value, a standard deviation of 1.0, and an alpha error level of 5%. In order to expand the protocol treatment base and increase the rate of accrual while maintaining the objectives of the protocol, the study, which was initially limited to patients with stage IIIC ovarian cancer, is being expanded to patients with Stage III/IV disease. In the SEER database: 1988-2001(Kosary 1988-2001), women with Stage IIIC disease comprised 19.4% of the ovarian cancer population; those with Stage III inclusive, 35.3%; and those with Stage IV, 31.7%. Thus, the eligibility expansion increases the base catchment population from 19.4% of women with ovarian cancer to 67% of which only a subset will meet protocol criteria.

In the completed Phase I study of Vigil™ vaccine in patients with solid tumors experiencing progressive disease following prior therapy, 50% of patients with serial assessments (n=18) demonstrated conversion from  $\gamma$ IFN ELISPOT

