negative to positive by Month 4 (Senzer N 2012). The percent  $\gamma$ IFN ELISPOT conversions and the timing thereof will be recorded in the current patient population of patients with minimal or no residual disease using descriptive statistics to assess the hypothesis that there is an inverse relationship between tumor volume and immune responsiveness based in part on the quantitative relationship between tumor volume and the production of immunosuppressive factors.

Although all patients will be evaluated for RFS, subgroup analyses will be separately performed on patients with negative ELISPOT at baseline and those with positive ELISPOT at baseline.

**Table 6:** Statistical Power of 2:1 Randomization Trial per Surgical Stage Stratification Group (1 tailed t test)

Surgical Stage Stratification	Vigil™ Vaccine (TTR in months)	Observation Control (TTR in months)	Power	n
Stage III patients with optimal (< 1 cm residual)	26.4	24	1.0	30
Stage IV or suboptimal (> 1 cm residual) stage III disease	17.6	16	1.0	30

Exploratory analysis of two Phase III studies (D9901 and D9902) with the recently FDA approved Provenge documented prolonged survival benefits in Provenge-treated prostate cancer patients (25.9 months vs. 21.4 months and 25.8 vs. 21.7 months, respectively). Supporting our clinical objective, patients who subsequently received docetaxel experienced a median survival of 34.5 months compared to 25.4 months in patients treated with placebo followed by docetaxel. Descriptive statistics will be employed to format the response rates and response durations to 2nd line therapy in patients that relapse in both FANG™ and observational groups.

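### The randomized arms were compared on time to recurrence and randomization ended on the result, but Section 13.1 still offers one undivided one-tailed 5% level and does not separate randomized from later non-randomized patients

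*Combined protocol and SAP*

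**What the plan says.** **The look and the change.** The Summary in the Synopsis gives a by-arm result, "Given the preliminary Phase II evidence of prolongation of time to relapse in randomized Vigil™ vs. No Vigil™ treated patients", with p=0.005. As a consequence of the amendment, patients screening for the main part of the trial "will receive Vigil™ vaccine and will no longer be randomized". It gives no data cut-off, number of patients or events, test, or sidedness. Time to recurrence (TTR) is the only primary objective (Synopsis; Section 3.1). I take time to relapse to be the same endpoint, and the result to come from this trial, since the same sentence uses it to change this trial's design.

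**The statistical section.** Section 13.1 still asks whether the vaccine "results in prolonged time to recurrence (TTR) compared with standard of care observation". Its power calculation was run "to conduct a 1-tail test of a sample average in comparison to the historical value", with "a standard deviation of 1.0, and an alpha error level of 5" percent. Table 6 is titled "Statistical Power of 2:1 Randomization Trial per Surgical Stage Stratification Group (1 tailed t test", with the bracket closing there. The stated purpose is that "a 10% increase in RFS (i.e. TTR) would provide adequate statistical power to support expanding the study".

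**What is absent.** Section 13 mentions no interim analysis, boundary or adjusted level. Sections 13.3 to 13.5 define endpoints without naming a test. Section 13.1 says that all patients will be evaluated for RFS, as a lead-in to ELISPOT subgroups. It does not separate patients enrolled before the look from those enrolled after it.

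**The concern.** A comparison of the primary endpoint by arm that changes the design is an interim look, whatever it is called. A later test of the same comparison at the full 5% gives a second chance of a positive result, unless the look could not have counted as one. The plan says neither.

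There is a second gap. Patients entering after the amendment all receive vaccine and have no concurrent control. Nothing in Section 13.1 keeps them out of the vaccine side of the comparison with observation. Adding them would turn a randomized comparison into a partly non-randomized one.

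At stake is how the final TTR result is read. Section 13.1 ties it to expanding the study, and the Synopsis mentions a Phase II/III protocol that it would naturally inform. A positive result would be read against 5% because no other level is given.

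**Working it through.** **1. The plan's own figure.** Inputs from Section 13.1 and Table 6: differences 26.4 − 24 = 2.4 and 17.6 − 16 = 1.6 months, SD 1.0, n = 30 per stratum, one-tailed 5% (critical value 1.645).

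- One sample against a historical value, Φ(δ√30/1.0 − 1.645): Φ(13.15 − 1.645) = 1.000 and Φ(8.76 − 1.645) = 1.000.
- Two samples at 2:1 (20 and 10), standard error √(1/20 + 1/10) = 0.387: Φ(2.4/0.387 − 1.645) = 1.000 and Φ(1.6/0.387 − 1.645) = 0.994.

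Table 6's power of 1.0 is reproduced. It is computed for one analysis at an undivided 5%.

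**2. Overall error with one look and one final test.** Let t be the information fraction at the look. Under no effect, the look statistic Z1 and the final statistic Z2 are bivariate normal with correlation √t. With critical value c1 at the look and 1.645 at the end, the overall one-sided error is 1 − P(Z1 < c1, Z2 < 1.645). Neither t nor c1 is in the documents, so both are varied.

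| t (assumed) | look could count at one-sided 5% | look could count only at one-sided 0.005 |
|---|---|---|
| 0.2 | 0.0893 | 0.0533 |
| 0.3 | 0.0863 | 0.0526 |
| 0.5 | 0.0801 | 0.0515 |
| 0.7 | 0.0729 | 0.0505 |
| 0.8 | 0.0686 | 0.0501 |

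**3. Levels that hold 5%.** With 0.025 at each of two looks, the overall error is at most 0.025 + 0.025 = 0.05 at any t. The exact equal level runs from 0.0272 (t = 0.2) to 0.0358 (t = 0.8), so 0.025 is somewhat conservative. If only 0.005 was spent at the look, the level left for the final test is 0.0467 to 0.0499 over the same range.

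**4. Why the early estimate is likely overstated.** An estimate that prompts a design change is selected for being large. As an illustration, assume 10 to 20 events at the look and one-sided p=0.005 (z = 2.576). At 2:1 the information is 2D/9 for D events, so the observed hazard ratio is exp(−2.576/√(2D/9)): 0.18 for D = 10 and 0.30 for D = 20. The planned 10% gain is a hazard ratio of 1/1.1 = 0.91 if TTR is exponential. Under that effect, p of 0.005 or less has probability 0.0075 (D = 10) or 0.0088 (D = 20). The event counts and the exponential form are my assumptions.

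**The case against.** **No final test is stated.** The 5% is an input to a power calculation against a historical mean, and no TTR test is named. The primary objective in the Synopsis and Section 3.1 is not comparative at all. On this view the comparative text is left over from before randomization ended, and an unspecified test cannot be said to miss its level. This stands as a limit: the point is conditional on the 5% being used. It does not remove the point, because Section 13.1 still states the comparison as the study's aim and offers no other level.

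**The inflation may be negligible.** If the look could have counted only at 0.005, the error is 5.0% to 5.3%. That stands. No such rule is written, so it cannot be assumed.

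**A level set now is retrospective.** The number of looks is unknown, and any threshold is chosen after p=0.005 was seen. That also stands, and it is why a descriptive label is an acceptable alternative.

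**Stronger readings that a reader might infer, and that the documents do not support:**

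- *The look was unplanned.* Only the current text is available. It describes no interim analysis; earlier versions cannot be seen. That it was unblinded adds little in an open-label trial.
- *The early result is counted twice.* No pooling rule is written, and any group-sequential final analysis includes its interim data.
- *Carry-over measures the false-positive rate.* Given one-sided p=0.005 at the look and no effect afterwards, a final 5% test succeeds with probability 0.39, 0.60 and 0.82 at t = 0.3, 0.5 and 0.7. These are conditional probabilities, and a planned, controlled design shows the same pattern. At a final level of 0.025 they are still 0.26, 0.42 and 0.64.
- *Later patients can confirm the finding.* They have no concurrent control, so they cannot confirm a randomized effect.

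The Synopsis already calls the evidence preliminary and leaves a more definitive answer to another protocol. This lowers the confirmatory weight but does not say how this trial's TTR comparison is to be read.

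**Conclusion.** The concern holds in a conditional form. The primary endpoint was compared by randomized arm, the result ended randomization for newly screened patients, and Section 13 takes no account of it. If the only level given is applied to a final randomized comparison, the overall one-sided error is about 7% to 9% where the look could have counted as success at 5%, and about 5.0% to 5.3% where it could have counted only at 0.005. These ranges assume one look, a final test at one-sided 5%, and t between 0.2 and 0.8. More looks at 5% would raise the first range. A flat statement that the error rate exceeds 5% by a known amount would go beyond the documents.

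Separately, and whatever the inflation, the plan has no rule that confines the vaccine-versus-observation comparison to randomized patients. This should be corrected before the final analysis. It does not invalidate the trial.

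**What to change.** Amend Section 13.1 as follows.

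1. Record the look: data cut-off, events per arm, test, sidedness, number of looks taken, and whether it was pre-specified.
2. Restrict the vaccine-versus-observation TTR comparison to patients who were randomized, and name the test. Either judge it at one-sided 5% divided by the number of looks (0.025 for two looks, which holds 5% at any information fraction) or label it descriptive. In both cases give the hazard ratio and confidence interval at mature follow-up.
3. Report TTR in the non-randomized post-amendment patients separately and descriptively. Do not pool it into the randomized comparison or use it to confirm that comparison.
4. Label the estimate behind p=0.005 as preliminary and likely overstated.

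The cost is wording and one extra table by cohort, with no added patients or visits. The price is a stricter final threshold (0.025 instead of 0.05 for two looks), or giving up a formal test if the descriptive route is taken.

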**Objective(s):****Primary Objectives:**

- To assess time to recurrence (TTR) following the administration of bi-shRNAfurin and GMCSF autologous tumor cell (Vigil™) vaccine.

**Secondary Objectives:**

- To identify and determine the effect of Vigil™ autologous tumor cell vaccine on immune surrogate markers.
- To assess the predictive potential of initial tumor infiltrating lymphocyte (TIL) and tumor associated macrophage (TAM) phenotypes.
- To enlarge the safety database of Vigil™ autologous tumor cell vaccine in patients with minimal disease.

**Methodology:**

This is a Phase II open-label trial of Vigil™ autologous tumor cell vaccine. Tumor will be harvested at the time of surgical debulking (standard of medical care).

Patients achieving clinical complete response (CR) following primary surgical debulking and doublet chemotherapy will be stratified for i) surgical stage (Stage IV or suboptimal debulking (>1 cm residual) Stage III disease versus Stage III patients with optimal debulking (<1 cm residual)) and ii) post-operative chemotherapy, pre-vaccine CA-125 of greater than 10 but less than or equal to 20 U/mL versus 0≤10 U/ml then randomized 2:1 (Note: patients with Stage IIIC ovarian cancer will be additionally evaluated as a subset using descriptive statistical endpoint only). Patients will receive  $1.0 \times 10^7$  cells / intradermal injection of gene transfected autologous tumor cells, Vigil™, once a month for up to 12 doses as long as sufficient material is available. A minimum harvest aliquot to produce 4 monthly injections will be required for entry into the study. These patients will be managed in an outpatient setting. Hematologic function, liver enzymes, renal function and electrolytes will be monitored monthly. Immune function analysis including ELISPOT analysis of cytotoxic T cell function to autologous tumor antigens will be monitored at (≤24 hours before) tissue harvest, ≤24 hours before the first cycle chemotherapy (post debulking), ≤24 hours before the third cycle chemotherapy (post debulking), baseline (screening); prior to Vigil™ injection at Months 2, 4, 6 and EOT. CA-125 will be monitored at baseline, every month for the first year, every 3 months ± 2 weeks for the second and third year.

**Number of Patients:** Approximately fifty (50) patients with high risk Stage III/IV ovarian cancer.

**Inclusion Criteria:**

1. Histologically confirmed Stage III/IV papillary serous or endometrioid ovarian cancer.
2. Per Amendment #8, treatment naïve, high risk ovarian cancer will no longer be stratified, but the following information will be collected:
  - a. Stage IV or suboptimal ( $>1$  cm residual) Stage III disease versus Stage III patients with optimal ( $\leq 1$  cm residual) disease,
  - b. CA-125  $\leq 10$  U/ml versus CA-125 greater than 10 to 20 U/ml
  - c. IP chemotherapy versus IV chemotherapy
3. Clinically defined CR (no cancer related symptoms, normal physical examination and CT scan abdomen/pelvis and chest x-ray, and CA-125  $\leq 20$  U/ml) following completion of surgical debulking. Patients enrolled must complete at least 5 but no more than 6 cycles platinum/taxane adjuvant or interval debulking + chemotherapy (or chemotherapy as per recommendations of NCCN guidelines, category 1 (IP chemotherapy included)). (Patients who complete surgery/chemotherapy with a CA-125  $>20$  U/mL pre-randomization have the option of being followed up to 2 months if serial CA-125 values continue to decrease at a rate of  $\geq 50\%$  per month.
4. Availability of "golf-ball" size  $\sim 10$ -30 grams tissue at time of primary surgical debulking.
5. Successful manufacturing of 4 vials of Vigil™ vaccine.
6. Recovered from all clinically relevant toxicities related to prior protocol specific therapy (including neuropathy  $\leq$ Grade 2).
7. ECOG performance status (PS) 0-2 prior to tumor debulking laparotomy.
8. ECOG PS 0-1 prior to Vigil™ vaccine administration.
9. Normal organ and marrow function as defined below:

Absolute granulocyte count	$\geq 1,500/\text{mm}^3$
Absolute lymphocyte count	$\geq 200/\text{mm}^3$
Platelets	$\geq 75,000/\text{mm}^3$
Total bilirubin	$\leq 2 \text{ mg/dL}$
AST(SGOT)/ALT(SGPT)	$\leq 2x$ institutional upper limit of normal
Creatinine	$< 1.5 \text{ mg/dL}$

10. Patients must be off all "statin" drugs for  $\geq 2$  weeks prior to initiation of therapy. Ability to understand and the willingness to sign a written informed consent document for tissue harvesting.
11. Ability to understand and the willingness to sign a written informed protocol specific consent.

**Exclusion Criteria:**

1. Surgery involving general anesthesia, radiotherapy, or immunotherapy within 4 weeks prior to randomization. Chemotherapy within 3 weeks prior to Vigil™ vaccine administration. Steroid therapy within 1 week prior to vaccine administration.
2. Patients must not have received any other investigational agents within 4 weeks of Vigil™ vaccine administration.

3. Patients with history of brain metastases.
4. Patients with compromised pulmonary disease.
5. Short term (<30 days) concurrent systemic steroids  $\leq 0.25$  mg/kg prednisone per day (maximum 7.5 mg/day) and bronchodilators (inhaled steroids) are permitted; other steroid regimens and/or immunosuppressives are excluded.
6. Prior splenectomy.
7. Prior malignancy (excluding nonmelanoma carcinomas of the skin and carcinoma *in situ* cervix) unless in remission for  $\geq 2$  years.
8. Kaposi's Sarcoma.
9. Uncontrolled intercurrent illness including, but not limited to ongoing or active infection, symptomatic congestive heart failure, unstable angina pectoris, cardiac arrhythmia, or psychiatric illness/social situations that would limit compliance with study requirements.
10. Patients with known HIV.
11. Patients with chronic Hepatitis B and C infection.
12. Patients with uncontrolled autoimmune diseases.

**Medication and Doses:** Autologous Vigil™ vaccine will be supplied by Gradalis, Inc.

Patients will receive  $1.0 \times 10^7$  cells via intradermal injection one day each month,  $\geq 3$  weeks following completion of doublet chemotherapy (no longer than 2.5 months post chemotherapy), for a maximum of 12 doses as long as sufficient material is available and subject is clinically stable.

**Duration:** If sufficient material is available, the patient may continue therapy up to 12 doses, unless disease progression is documented (see Section 4.0, Study Design). If the patient experiences  $\geq$  Grade 2 toxicity (excluding Grade 3 injection site reaction), they may continue on treatment with doses delayed or reduced if, in the opinion of the PI, this is considered to be in the best interest of the patient.

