## 4.0 STUDY DESIGN

### 4.1 Design

This is a Phase II open-label trial of maintenance Vigil™ autologous tumor cell vaccine. Tumor will be harvested at the time of surgical debulking (standard of medical care). Subsequently, patients achieving clinical CR following primary surgical debulking and doublet chemotherapy will be stratified for i) surgical stage (Stage IV or suboptimal debulking (>1 cm residual) Stage III disease versus Stage III patients with optimal debulking (<1 cm residual)) and ii) post-op chemotherapy, pre-vaccine CA-125  $>10 \leq 20$  U/mL versus  $0 \leq 10$  U/ml, then randomized 2:1 (Note: patients with Stage IIIC ovarian cancer will be additionally evaluated as a subset using descriptive statistics only). Patients will receive  $1.0 \times 10^7$  cells / intradermal injection of gene transfected autologous tumor cells, Vigil™, once a month for up to 12 doses as long as sufficient material is available. Enough harvested tissue to provide a minimum of 4 monthly injections will be required for entry into the study. These patients will be managed in an outpatient setting. Hematologic function, liver enzymes, renal function and electrolytes will be monitored monthly. Immune function analysis including

ELISPOT analysis of cytotoxic T cell function to autologous tumor antigens will be monitored at ( $\leq$ 24 hours before) tissue harvest,  $\leq$ 24 hours before the first cycle of chemotherapy (post debulking),  $\leq$ 24 hours before the third cycle of chemotherapy (post debulking), baseline (screening), prior to Vigil™ injection Months 2, 4, 6 and at EOT. The dates of the last dose of chemotherapy and the administration of Vigil™ vaccine #1 will be recorded.

Treatment will be continued until disease recurrence or exhaustion of the patient's vaccine supply. If  $\geq$  Grade 2 toxicity by NCI Common Toxicity Criteria (excluding Grade 2 fever  $\leq$  24 hours and Grade 2 and 3 injection site reactions) develops related to study treatment the vaccine dose will be reduced by 50% and continued on a monthly basis. If a single patient develops  $\geq$  Grade 3 toxicity (other than injection site reaction) related to study treatment the trial will be placed on hold for reevaluation of design in discussion with FDA. During this hold, no new subjects will initiate dosing, but subjects already being dosed may continue dosing as scheduled if deemed clinically appropriate by the PI.

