#### **5.4 Withdrawal**

#### **Off Study Treatment**

Patients will be taken **off study treatment** if any of the following occur:

1. The patient experiences unacceptable ( $\geq$ Grade 3) toxicity felt to be related to treatment with the tumor cell vaccination that persists for  $>1$  week.
2. Persisting Grade 3 or 4 toxicity unrelated to treatment, defined as failing to normalize within 4 weeks.
3.  $\geq$  Grade 2 allergic reactions related to the study agent.
4. Grade 2 autoimmune reactions unless there is evidence of clinical benefit.
5.  $\geq$  Grade 3 autoimmune reactions.
6. An intercurrent illness, which would in the judgment of the investigator, affects assessments of clinical status to a significant degree or requires discontinuation of study treatment.

7. Non-protocol therapy (including, but not limited to, chemotherapy not listed as Level 1 Category of Evidence per NCCN Guidelines Version 3.2012, radiotherapy, hormonal therapy, immunotherapy, or surgery) is administered during study treatment.
8. Non-compliant with protocol or treatment.
9. Patient refuses to continue treatment.

The date of and reason for discontinuation must be noted in the Case Report Form (CRF). Every effort should be made to complete the appropriate assessments.

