### **Treatment Delay**

1. Treatment may be delayed no more than 4 weeks to allow recovery from toxicity.
2. Patients who delay treatment for more than 4 weeks due to toxicities will be considered off study treatment (see Section 4.4 Off Study Treatment).
3. Treatment delay not related to toxic events (including subjects unable to adhere to monthly injection) will not be delayed for more than three days. Unless a delay due to symptoms related to disease or infection in which case up to a 2 week delay is allowed.
4. If  $\geq$  one 2 week delay due to disease or infection occurs, patient status must be reviewed by sponsor.
5. If patients miss doses due to toxicities, the doses will be made up the following week and continue on a revised monthly schedule thereafter.

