### **Dose Modification for Toxicity**

If  $\geq$  Grade 2 toxicity by NCI Common Toxicity Criteria (excluding Grades 2 and 3 injection site reactions) develops related to study treatment the vaccine dose will be reduced by 50% and continued on a monthly basis. If a single patient develops  $\geq$  Grade 3 toxicity (other than site reaction) related to study treatment the trial will be placed on hold for re-evaluation of design in discussion with FDA.

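### The Synopsis, Section 4.1 and Section 6.4 give conflicting rules for dosing after Grade 2 or higher toxicity, and nothing says which governs

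*Combined protocol and SAP*

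**What the plan says.** Four places in the protocol bear on dosing after toxicity.

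- **Synopsis, Duration.** The trigger is Grade 2 or higher: "Grade 2 toxicity (excluding Grade 3 injection site reaction". No causal link to the vaccine is required. The action is permissive: "they may continue on treatment with doses delayed or reduced if, in the opinion of the PI, this is considered" to be best for the patient. No size of reduction is given.
- **Section 4.1, Design.** The trigger is "Grade 2 toxicity by NCI Common Toxicity Criteria (excluding Grade 2 fever" of 24 hours or less and Grade 2 and 3 injection site reactions). If such toxicity "develops related to study treatment the vaccine dose will be reduced by 50% and continued on a monthly basis". No investigator discretion is stated.
- **Section 6.4, Dose Modification for Toxicity.** The action is the same as in 4.1, with a shorter list of exemptions: "excluding Grades 2 and 3 injection site reactions) develops related to study treatment the vaccine dose will be reduced by 50" percent. Fever is not mentioned.
- **Section 6.4, Treatment Delay.** "Treatment may be delayed no more than 4 weeks to allow recovery from toxicity". The text does not connect this to the 50% reduction.

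**The concern.** These are operating rules that a site applies at the bedside, and they differ in who decides, what triggers a change and what is exempt. If two sites follow different pages, the same event can lead to different doses. Monitors would also lack a single standard for deciding whether either site had deviated.

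This matters for what the trial sets out to describe. Enlarging the safety database is a secondary objective (Section 3.2), and the Synopsis says that more safety data are needed in ovarian cancer patients given 1 x 10^7 cells monthly. Dose received, counts of dose reductions and the safety description at the protocol dose all depend on how the rule is read. A halved dose is 0.5 x 10^7 cells, which is below both dose levels that the Synopsis lists for Phase I (1.0 and 2.5 x 10^7).

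**Working it through.** The plan states no figure to reproduce, so the check is a comparison of the texts followed by simple arithmetic on dose.

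**Step 1. The three dosing rules side by side**

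| Feature | Synopsis, Duration | Section 4.1 | Section 6.4, Dose Modification |
|---|---|---|---|
| Status of the change | At PI opinion | Compulsory | Compulsory |
| Size of reduction | Not stated | 50% | 50% |
| Relatedness needed | No | Yes | Yes |
| Injection site reactions exempt | Grade 3 only | Grades 2 and 3 | Grades 2 and 3 |
| Grade 2 fever of 24 hours or less exempt | No | Yes | No |

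**Step 2. Apply the rules to specific events**

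- *Related Grade 2 event, not exempt anywhere.* The Synopsis lets the PI delay or reduce by any amount. Sections 4.1 and 6.4 require halving. Treatment Delay also permits up to 4 weeks' postponement, but does not say whether halving still follows.
- *Unrelated Grade 2 event.* The Synopsis rule applies. The 4.1 and 6.4 rule is not triggered.
- *Grade 2 injection site reaction.* The Synopsis rule applies. Sections 4.1 and 6.4 exempt it.
- *Grade 3 injection site reaction.* All three exempt it. Read literally, then, the Synopsis catches the milder reaction and passes over the worse one ("excluding Grade 3 injection site reaction").
- *Related Grade 2 fever of 24 hours or less.* Section 6.4 requires halving, while Section 4.1 leaves the scheduled dose in place. This conflict lies within the body of the protocol and does not involve the Synopsis.

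Some events fall outside the comparison because Section 5.4 takes the patient off treatment, for example from grade 2 upwards for "Grade 2 allergic reactions related to the study agent". None of the three dosing rules mentions that carve-out.

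**Step 3. Look for a rule of precedence**

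None is stated. The Duration paragraph does refer to Section 4.0, but in the sentence on continuing to 12 doses unless disease progresses, not in the sentence on toxicity.

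**Step 4. Size per affected patient (illustration)**

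Inputs: 1.0 x 10^7 cells per injection (Section 9.2, Preparation) and 4 to 12 doses (Section 6.4, Vaccination Schedule and Dose). Assume one event after dose k of n, a single halving that persists, and all remaining doses given. In full-dose units:

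- Compulsory halving: D = k + 0.5 x (n - k).
- Delay only, the largest total that the Synopsis wording allows: n.
- Ratio: D / n = 0.5 + 0.5 x k / n.

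| n | k | D | Ratio to n |
|---|---|---|---|
| 12 | 1 | 1 + 0.5 x 11 = 6.5 | 54% |
| 12 | 11 | 11 + 0.5 x 1 = 11.5 | 96% |
| 4 | 1 | 1 + 0.5 x 3 = 2.5 | 62.5% |
| 4 | 3 | 3 + 0.5 x 1 = 3.5 | 87.5% |

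The widest gap is 6.5 x 10^7 against 12 x 10^7 cells. It narrows as the event comes later or the vaccine supply is smaller.

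**Step 5. Frequency**

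This cannot be calculated. Section 1.10 names injection site erythema as the most common related event in Phase I but pools Grades 1 and 2. No Grade 2 rate is given for this population.

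**The case against.** The strongest reply is that a synopsis is a summary. Its sentence can be read as permission to stay on treatment rather than as a dosing rule, and a reduction of unstated size is compatible with 50%. Two body sections agree that halving is required, and the Synopsis mentions Section 4.0 one sentence earlier. On that view a site has enough to go on.

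Part of this stands. A reader might infer that resuming full dose after a related, non-exempt Grade 2 event is as compliant as halving. The documents do not support that, because full dosing would breach both 4.1 and 6.4. A reader might also infer that delay for toxicity exists only in the Synopsis. It does not, since Treatment Delay in 6.4 provides for it too. On the first feature, therefore, the conflict is about discretion and the size of the reduction, not about whether delay is available.

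The reply does not reach the rest. Missing detail does not explain a different causal trigger or a different list of exempt injection-site grades. The fever mismatch lies between two body sections, so no appeal to the Synopsis being a summary can settle it.

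On impact, Section 1.10 reports no significant toxic effect and two possibly related Grade 3 events, and Section 11.3 calls side effects minimal. These statements caution against assuming that many patients are affected, but they give no Grade 2 rate.

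**Conclusion.** The inconsistency is real and should be corrected. The rules differ on obligation, size of reduction, relatedness, exempt injection-site grades and short-lived Grade 2 fever, and the place of delay is left open. The dose given after the same event, and whether it counts as a deviation, can depend on the page that a site follows.

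For one patient the compulsory cut gives between 54% and 96% of the delay-only total with 12 doses, and between 62.5% and 87.5% with 4, under the assumptions in the working. These are bounds per affected patient, not expected effects on the trial.

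Three stronger readings are tempting but unsupported. Because injection site reactions are the most frequent expected effect, a reader might infer that many patients would be dosed differently; the pooled Grade 1 and 2 reporting does not show this. A reader might infer that correcting the Synopsis alone is enough; it would leave 4.1 and 6.4 in conflict on fever. A reader might infer a bias in time to recurrence; nothing in the documents links these dose differences to that outcome.

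**What to change.** Reconcile Synopsis (Duration), Section 4.1, Section 6.4 (Treatment Delay) and Section 6.4 (Dose Modification for Toxicity) into one dose-modification text. The Synopsis and 4.1 should then repeat it word for word or refer to it. The single text should state once:

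- whether the change is compulsory or at PI discretion, and its size;
- whether the toxicity must be related to the vaccine;
- which injection-site grades and which fever events are exempt;
- whether delay replaces the reduction or accompanies it.

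The sponsor decides the clinical content of each item; this review takes no position on it.

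The cost is small: a text change in four places. It may not be purely editorial. Section 7.5 requires a formal amendment, with sponsor, IRB or IEC, and IBC approval, for changes that affect study procedures, and allows a memorandum only for minor clarifications. Settling compulsory against discretionary dosing could fall in the first group.
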